6.13 Exploratory Endpoints

6.13.1 Survival at day 7, 14, 21, 28 and 90

Survival time will be derived as:

(Death date/last date patient known to be alive – date of randomisation + 1).

Survival time will be analysed with a Cox proportional hazards model including covariates for treatment group and baseline MELD score. Tied observations will be

handled using the Breslow-Henshaw method. The assumption of proportional hazards will be assessed visually using the log-log plot.

Estimates for the hazard ratio (DS102:Placebo), associated 95% CI and p-values will be presented.

Estimates of survival rate and associated 95% CI at days 7, 14, 21, 28 and 90 will be presented for each treatment group.

Kaplan-Meier plot of the probability of survival against time (days) will be presented for each treatment group.

6.13.2 Change in GT from baseline to day 7, 14, 21 and 28

Gamma glutamyl transferase is a liver enzyme indicative of liver dysfunction and alcohol intake.

6.13.2.1 Analysis

Change in GT from baseline up to and including day 28 will be assessed with an MMRM analysis, using the FAS, including terms for treatment group, visit, treatment-by-visit as fixed effects and the baseline GT value as a covariate. The adjusted treatment means and adjusted mean difference between the active dose and placebo will be presented along with 95% CI and p-value for the day 7, 14, 21 and 28 timepoint.

The modelling process described in section 6.11.1 will be followed.

6.13.2.2 Descriptive summaries and listing

Covered under section [16.7](#).

6.13.3 Change in ALT from baseline to day 7, 14, 21 and 28

Alanine aminotransferase is liver enzyme and a marker of liver injury.

6.13.3.1 Analysis

Change in ALT from baseline up to and including day 28 will be assessed with an MMRM analysis, using the FAS, including terms for treatment group, visit, treatment-by-visit as fixed effects and the baseline ALT value as a covariate. The adjusted treatment means and adjusted mean difference between the active dose and placebo will be presented along with 95% CI and p-value for the day 7, 14, 21 and 28 timepoint.

The modelling process described in section 6.11.1 will be followed.

6.13.3.2 Descriptive summaries and listing

Covered under section [16.7](#).

6.13.4 Change in Child-Pugh score from baseline to day 7, 14, 21 and 28

The Child-Pugh score is a means of assessing the severity of chronic liver disease, including cirrhosis, based on five clinical parameters (bilirubin, albumin, INR, ascites and hepatic encephalopathy) scored on a scale of 1 to 3. A total score is which indicates the severity and prognosis of chronic liver disease is then derived.

6.13.4.1 Analysis

Change in Child-Pugh score from baseline up to and including day 28 will be assessed with an MMRM analysis, using the FAS, including terms for treatment group, visit, treatment-by-visit as fixed effects and the baseline Child-Pugh score as a covariate.

The adjusted treatment means and adjusted mean difference between the active dose and placebo will be presented along with 95% CI and p-value for the day 7, 14, 21 and 28 timepoint.

The modelling process described in section 6.11.1 will be followed.

6.13.4.2 Descriptive summaries and listing

Child-Pugh score observed values, absolute change from baseline and percentage change from baseline will be listed and summarised by treatment group and visit.

6.13.5 Change in APACHE-II score from baseline to day 7, 14 , 21 and 28

The acute physiologic and chronic health evaluation II score will assess patients for the presence of multiple organ dysfunction and predict mortality by generating a point score ranging from 0 to 71 based on twelve physiologic variables, age and underlying health.

6.13.5.1 Analysis

Change in APACHE-II score from baseline up to and including day 28 will be assessed with an MMRM analysis, using the FAS, including terms for treatment group, visit, treatment-by-visit as fixed effects and the baseline APACHE-II value as a covariate. The adjusted treatment means and adjusted mean difference between the active dose and placebo will be presented along with 95% CI and p-value for the day 7, 14, 21 and 28 timepoints.

The modelling process described in section 6.11.1 will be followed.

6.13.5.2 Descriptive summaries and listing

APACHE-II score observed values, absolute change from baseline and percentage change from baseline will be listed and summarised by treatment group and visit.

6.13.6 Change in Lille score from baseline to day 7, 14, 21 and 28

The Lille score is a composite score which predicts mortality in patients with AH who are not responding to steroid therapy. It is based on age, albumin, bilirubin (initial), bilirubin (day 7), creatinine and prothrombin time. A score of > 0.45 identifies 75% of deaths, a score of > 0.45 predicts a 6-month survival of 25% and a score of < 0.45 predicts survival of 85%.

6.13.6.1 Analysis

Change in Lille score from baseline up to and including day 28 will be assessed with an MMRM analysis, using the FAS, including terms for treatment group, visit, treatment-by-visit as fixed effects and the baseline Lille score as a covariate. The adjusted treatment means and adjusted mean difference between the active dose and placebo will be presented along with 95% CI and p-value for the day 7, 14, 21 and 28 timepoints.

The modelling process described in section 6.11.1 will be followed.

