#### 9.1.10 Lille Score

The Lille score is a composite score which predicts mortality in patients with AH who are not responding to steroid therapy. It is based on age, albumin, bilirubin (initial), bilirubin (day 7), creatinine and PT; a score of >0.45 identifies 75% of deaths, a score of >0.45 predicts a 6-month survival of 25%, and a score of <0.45 predicts survival of 85%.

Lille score will be assessed at Visit 2/Baseline, Visit 3/Day 3, Visit 4/Day 5, Visit 5/Day 7, Visit 6/Day 14, Visit 7/Day 21, Visit 8/Day 28/Early Termination and Visit 9/Day 90/Follow up.

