2.2 Study Endpoints

The primary endpoint of the study is:

- Percentage change in Model End-stage Liver Disease (MELD) score from baseline to Day 28.

The secondary endpoints are:

- Change in total bilirubin from baseline to Day 7, 14, 21 and 28
- Proportion of patients showing a 25% reduction of bilirubin at day 7, 14, 21, and 28
- Change in serum Cytokeratin 18-M30/M65 from baseline to Day 7, 14, 21 and 28
- Change in Aspartate Transaminase (AST) levels from Baseline to Day 7, 14, 21 and 28
- Change in AST: Alanine Transaminase (ALT) ratio from Baseline to Day 7, 14, 21, 28
- Change in Maddrey Discriminant Function (MDF) score from baseline to Day 7, 14, 21 and 28

- Proportion of patients showing a 25% reduction in MELD score from baseline to Day 7, 14 and 21
- Change in MELD score from baseline to Day 7, 14 and 21
- Change in modified sequential organ failure assessment (m-SOFA) from baseline to Day 7, 14, 21 and 28
- Proportion of patients with a 2-point worsening of m-SOFA from baseline at Day 7, 14, 21 and 28
- Change in hepatic encephalopathy as assessed by West Haven criteria, from baseline at Day 7, 14, 21 and 28
- Incidence of acute kidney injury over 28 days (defined by requiring medicinal or mechanical support)
- Incidence of variceal haemorrhage, ascites or hepatic encephalopathy over 28 days

The exploratory endpoints are:

- Survival at day 7, 14, 21, 28 and 90 using Kaplan-Meier Plot
- Change in Gamma Glutamyl Transferase (GT) from baseline to Day 7, 14, 21 and 28
- Change in ALT from baseline to Day 7, 14, 21 and 28.
- Change in Child-Pugh score from baseline to Day 7, 14, 21 and 28
- Change in Acute Physiologic and Chronic Health Evaluation (APACHE) II score from baseline to Day 7, 14, 21 and 28
- Change in Lille score from baseline to Day 7, 14, 21 and 28

The safety endpoints are:

- Treatment emergent serious adverse events (SAEs), adverse events (AEs) and suspected unexpected serious adverse reactions (SUSARs)

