6.3 General Derivations

- Definition of baseline

Baseline is defined as the last non-missing value (including scheduled and unscheduled assessments) prior to the patient receiving study treatment.

- Incomplete dates

For calculation purposes, incomplete dates will be completed using worst case. Further details are detailed in the relevant sections as required.

- Non-numeric values recorded in a numeric field

In the case where a variable is recorded as “>x”, “ $\geq x$ ”, “ $<x$ ” or “ $\leq x$ ” in a numeric field, then for analysis purposes a value of x will be taken. Where a range of values is quoted the midpoint of the range will be taken. For example, if a laboratory safety parameter is reported as being below the limit of quantification or $< x$, the value of the limit will be used in the calculation of summary statistics. The recorded value will be reported in listings.

- Methods for handling withdrawals and missing data

Imputation of any data will be detailed in the relevant sections.

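### The Lille score as defined needs Day 7 bilirubin, so no baseline score exists for the planned change-from-baseline analysis

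*SAP*

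**What the plan says.** **Definition.** Protocol 9.1.10 says of the Lille score: "It is based on age, albumin, bilirubin (initial), bilirubin (day 7), creatinine and PT". SAP 6.13.6 gives the same list. Both add a 0.45 threshold for predicted survival. Neither gives a formula.

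**Schedule.** Protocol 9.1.10 continues: "Lille score will be assessed at Visit 2/Baseline, Visit 3/Day 3, Visit 4/Day 5, Visit 5/Day 7", followed by Days 14, 21, 28 and 90. The visit lists in Protocol 8.2 and the flow charts in Appendices 1 and 2 agree.

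**Baseline.** SAP 6.3: "Baseline is defined as the last non-missing value (including scheduled and unscheduled assessments) prior to the patient receiving study treatment".

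**Endpoint and analysis.** SAP 2.2 lists as exploratory "Change in Lille score from baseline to Day 7, 14, 21 and 28"; Protocol 5.3 has the same endpoint without Day 21. SAP 6.13.6.1 states: "Change in Lille score from baseline up to and including day 28 will be assessed with an MMRM analysis", on the FAS, with "the baseline Lille score as a covariate". SAP 6.13.6.2 adds by-visit summaries of observed values, absolute change and percentage change. Protocol 12.8.3 likewise takes the baseline level as covariate for exploratory variables.

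**Changes from the protocol.** SAP 6.25 returns to this endpoint only to add Day 21.

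**The concern.** A score built partly on Day 7 bilirubin cannot be known before the first dose. The analysis nevertheless uses a pre-dose value twice: as the reference for every change and as a covariate. Followed literally, the model has no analysable records. In practice a site or programmer would have to supply a rule, and different people could supply different ones.

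At stake is whether the Lille results mean anything. An invented baseline would give estimates, confidence intervals and p-values for a quantity that neither document defines, under the name of a score whose 0.45 threshold is quoted beside it.

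**Working it through.** The documents state no figure for the Lille endpoint. Their only sample-size figure concerns MELD, and it reproduces: a two-sample t-test with d = 0.54, two-sided alpha 0.05 and 80% power gives n = 54.81, rounded up to 55 per group, with power 0.8014 as in Protocol 12.3. It does not depend on Lille. The rest is a check of definitions against timing.

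**1. Notation.** Write the score as L = f(x, b0, b7). Here b0 is initial bilirubin, b7 is Day 7 bilirubin, and x stands for age, albumin, creatinine and prothrombin time. The documents date only the two bilirubin values. The function f is not given and is not needed below.

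**2. Is the score available at each scheduled visit?**

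| Visit | b7 available (nominal days)? |
|---|---|
| Baseline (Day 0) | No |
| Day 3 | No |
| Day 5 | No |
| Days 7, 14, 21, 28 | Yes |
| Day 90 | Yes |

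Up to Day 28 there are 1 + 6 = 7 assessments, of which 3 precede b7 (3/7 = 43%). Including Day 90 it is 3 of 8. The flow charts allow ±2 days at Day 7, so that sample could be drawn as early as Day 5. The window does not reach Day 0.

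**3. Combine with the baseline definition.** SAP 6.3 requires a value before study treatment. L needs b7, which is measured about a week later. The number of patients with a baseline L as defined is 0 of the 120 planned. The change L(v) − L(baseline) is then undefined at each of Days 7, 14, 21 and 28, and so is the covariate. Absolute and percentage change fail for the same reason.

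**4. Do the obvious workarounds help?** None is written in either document; each is an assumption made here.

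- *Use the Day 7 score as baseline.* The covariate is then measured after randomisation and may be affected by treatment, and it breaks SAP 6.3. If x is also held at its initial values, the change is f(x, b0, b7) − f(x, b0, b7) = 0 for every patient at every visit.
- *Re-measure x at each visit but keep b7.* Later scores can differ from the Day 7 score. A baseline score still needs b7, so step 3 is unchanged.
- *Replace b7 by the current visit's bilirubin, bv.* Baseline becomes f(x, b0, b0) and later visits f(x, b0, bv). This can be computed, but it is a different quantity. The documents quote 0.45 for the score with Day 7 bilirubin, not for this one.

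**5. Is the conflict resolved elsewhere?** Protocol 9.1.10 and SAP sections 2.2, 6.3, 6.13.6 and 6.25 contain no rule for a baseline Lille score and none that replaces Day 7 bilirubin.

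**The case against.** The strongest reply is that the gap is one of derivation. One sentence defining a visit-specific score would make the model run, and replacing the endpoint is then a choice. That is fair as far as it goes: a number can be produced. It would still be a modified score needing its own name and definition, and the 0.45 threshold could not be carried over without support.

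A reader might infer four stronger points that the documents do not support.

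- *That each patient has only one Lille score.* Only bilirubin is dated. Albumin, creatinine and prothrombin time are undated and come from laboratory panels taken at every visit, so scores at Days 14, 21 and 28 could differ from Day 7.
- *That the change would mostly re-express bilirubin change.* This needs the coefficients, and no formula is given.
- *That the early assessments can simply be dropped.* Protocol 11.3.1 lists a Lille score above 0.85 among its criteria for potential severe drug-induced liver injury. These lead to adjudication within 24 hours, and 11.3.1 does not say which visit's score applies. Removing assessments would touch that rule, so the sections must be reconciled first.
- *That the trial's main conclusions are at risk.* The primary MELD analysis, the sample size and the five-level ordinal variable do not use Lille.

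On the remedy, a Day 7 comparison depends on survival and a bilirubin sample to Day 7, so it needs stated rules for both. The documents describe the score for patients not responding to steroids, while steroid treatment is not an entry criterion. The 0.45 split is therefore best kept optional.

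**Conclusion.** The point holds. On the documents' own definitions of the score and of baseline, no baseline Lille score exists. The model in SAP 6.13.6.1 and the change summaries in 6.13.6.2 therefore have no valid baseline input for any of the 120 planned patients, and all four planned contrasts are affected. This is an analysis that fails when followed as written, which goes beyond missing detail.

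The conclusion rests on reading the Day 7 label on bilirubin literally, as both documents print it, and on applying SAP 6.3 to this endpoint, since no exception is stated. It needs no assumption about the formula or about when the undated components are taken. The consequence is limited: the endpoint is exploratory and is tested without multiplicity adjustment. It should be corrected before unblinding.

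**What to change.** **Endpoint and analysis.** In SAP 2.2 and 6.13.6 and Protocol 5.3 (with matching wording in the synopsis and Protocol 12.8.3), replace the change-from-baseline model and the change summaries with a between-arm comparison of the Day 7 Lille score on the FAS. Use a linear model with treatment and baseline MELD. Optionally add the proportion above 0.45 by logistic regression with the same terms.

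**Definitions to write down.**

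- The formula, and the visit from which each component is taken.
- Whether a bilirubin drawn within the ±2-day window counts as Day 7.
- How deaths and missing bilirubin before Day 7 are handled in each analysis.

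If the sponsor prefers a visit-specific modified score, the SAP should define it and its baseline explicitly, name it as a modification, and not apply the 0.45 threshold without support.

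**Reconciliation.** Leave the scheduled assessments in place until Protocol 9.1.10, 11.3.1 and Appendices 1 and 2 have been reconciled with the definition, including which score the 0.85 criterion refers to. That is for the sponsor and its clinical experts to decide.

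**Cost.** Wording in both documents and an entry in SAP 6.25. No new data are needed: bilirubin is already sampled at Baseline and Day 7 (Protocol 9.1.2), and albumin, creatinine and prothrombin time are in the laboratory panel (Protocol 9.2.5). Four exploratory contrasts become one, or two with the optional proportion. What is given up is the by-visit change, which has no defined baseline.

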6.13.6.2 Descriptive summaries and listing

Lille score observed values, absolute change from baseline and percentage change from baseline will be listed and summarised by treatment group and visit.

6.13.7 Combination of change of MELD score from baseline, premature treatment terminations and mortality

A 5-level ordinal variable combining change of MELD score from baseline, premature treatment terminations and mortality will be derived.

Each patient will be allocated to the lowest/worst level that occurred.

Level 1: death within 28 days using survival time derived in section [6.13.1](#)

Level 2: death within 90 days using survival time derived in section [6.13.1](#)

Level 3: early termination because of safety issues or lack of efficacy

Level 4: no improvement in MELD score at day 28 compared to baseline (classed as less than 25% reduction in MELD score from baseline to day 28).

Level 5: improvement in MELD score at day 28 compared to baseline (classed as greater than or equal to a 25% reduction in MELD score baseline to day 28).

Patients who are lost to follow up within 28 days and therefore do not have a day 28 MELD score will be allocated to level 4 or 5 depending on their imputed result at day 28 based on the model in section [6.11.1](#) under a missing at random (MAR) assumption.

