## 7.5 Withdrawal of Patients

Patients have the right to withdraw from the study at any time for any reason, without repercussion. The Investigator must explain this to the patient and that this will in no way prejudice their future treatment. The investigator also has the right to withdraw patients from the study if she/he feels it is in the best interest of the patient or if the patient is uncooperative or non-compliant. It is understood by all concerned that an excessive rate of withdrawal can render the study un-interpretable, therefore, unnecessary withdrawal of patients should be avoided. Should a patient decide to withdraw, all efforts will be made to complete and report the observations, particularly the follow-up examination, as thoroughly as possible.

In the event of patient withdrawal, the Investigator or one of his or her staff members should talk to the patient or in case of hospital discharge contact the patient either by telephone or through a personal visit to determine as completely as possible the reason for the withdrawal, and record the reason in patient's source document and case report form (CRF). A complete final early termination evaluation at the time of the patient's withdrawal should be made with an explanation of why the patient is withdrawing from the study. If the reason for removal of a patient is an adverse event (AE) or an abnormal laboratory test result, the principal specific event or test will be recorded.

Please note: the patient is allowed not to give a reason for withdrawal. If this is the case this must be recorded as well.

Patients who discontinue the study before Day 28 visit and are discharged from the hospital will be asked to come for an early termination visit as soon as possible and have the assessments listed at Day 28 performed. Mortality will be assessed throughout to Day 90.

There will be two main categories for withdrawals from the study: "complete withdrawal" and "withdrawals from investigational product".

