### 7.5.1 Complete Withdrawal

Discontinuation of investigational product and all efficacy and safety evaluations. Standard reasons for withdrawing from further participation in the study and from the follow-up visits may be:

- Patient's decision (withdrawal of consent to participate)
- Patient lost to follow-up

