### **12.8.3 Secondary variables**

The secondary and exploratory efficacy variables will be summarised with descriptive statistics per treatment group and visit. The change from baseline to Day 28 (and other visits) for the active treatment group will be compared against placebo either via logistic regression or analysis of covariance taking the baseline level as covariate into account. Survival time will be analysed using the Cox Proportional Hazards model including treatment group and MELD score at baseline as covariate. The 5% level of significance will be used for all treatment comparisons of secondary and exploratory endpoints without adjustment for multiplicity.

A new secondary efficacy variable will be a 5-level ordinal variable combining change of MELD score from baseline, premature treatment terminations and mortality as follows; each patient will be allocated to the first level that occurs

- level 1: death within 28 days,
- level 2: death within 90 days,
- level 3: early treatment termination because of safety issues or lack of efficacy,
- level 4: no improvement in Meld Score at day 28 compared to baseline,
- level 5: improvement in Meld Score at day 28 compared to baseline

Patients with lost to follow up within 28 days will be allocated to level 4 or 5 according to their imputed result at day 28 based on the model in 12.9.2 as for these patients the MAR assumption seems appropriate.

This ordinal variable will be analysed using ordinal logistic regression with MELD score as baseline covariate ( $\alpha=0.05$  two-sided). An odds ratio including 95%-confidence limits will be calculated as measure of effect size for this variable.

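### The five-level ordinal variable gives no level to some patients without a Day 28 MELD and cannot count a death among patients whose vital status is unknown

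*SAP*

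**What the plan says.** SAP 6.13.7 defines five levels, from death within 28 days (1) to a MELD reduction of at least 25% at Day 28 (5), and states that "Each patient will be allocated to the lowest/worst level that occurred". Level 3 is early termination for safety or lack of efficacy. Levels 1 and 2 each need a death, for example "Level 2: death within 90 days using survival time derived in section" 6.13.1. That section derives survival time from "Death date/last date patient known to be alive", so a patient without a recorded death is censored in the Cox model.

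One rule covers incomplete follow-up: "Patients who are lost to follow up within 28 days and therefore do not have a day 28 MELD score" are placed in level 4 or 5 from their imputed Day 28 result under MAR. Protocol 12.8.3 says the same, "Patients with lost to follow up within 28 days will be allocated to level 4 or 5", and gives the reason: "as for these patients the MAR assumption seems appropriate".

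Protocol 7.5.1 lists withdrawal of consent and loss to follow-up as two separate reasons for complete withdrawal, after which all evaluations stop. Protocol 7.5.2 covers patients who stop study drug but stay in follow-up. Protocol 7.5 adds that "Mortality will be assessed throughout to Day 90".

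**The concern.** The variable exists to put death and MELD on one scale, in a disease for which protocol 1.1 cites mortality above 30% (no time horizon given). The rule for incomplete data is narrower than the population it must classify, and it uses a model that produces MELD values but no deaths.

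Two things are at stake. First, the patients without a level would leave the regression according to their recorded reason for stopping, and a programmer would have to decide how to treat them. Second, patients with the least information about survival are placed where only survivors belong. If loss differs between arms, the arm with more loss gains.

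**Working it through.** **1. Where each patient without a recorded death goes**

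| Patient | Level under SAP 6.13.7 |
|---|---|
| Lost to follow-up before Day 28 | 4 or 5 from imputed MELD (stated) |
| Stopped for safety or lack of efficacy | 3 (stated) |
| Stopped study drug for another reason, stayed in follow-up, Day 28 MELD measured | 4 or 5 from observed MELD |
| Withdrew consent completely before Day 28 for another reason, or missed Day 28; no Day 28 MELD | None |
| Day 28 MELD measured, not reached at Day 90 | 4 or 5 (or 3), as for a confirmed survivor |

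No other section fills the fourth row. SAP 6.3 leaves imputation to the individual sections. SAP 6.13.7.1 has no rule for a missing outcome. SAP 6.11.1 enters early termination MELD at the next scheduled visit, so it can stand for Day 28 only after the Day 21 visit. In the first and last rows, levels 1 and 2 cannot be reached without a recorded death.

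**2. What the documents quantify**

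They give no power, sample size or loss rate for this variable. The only attrition figure is for the primary endpoint: 55 per group needed, 60 randomised. The 55 reproduces (noncentral t power 0.8014 for effect size 0.54, two-sided alpha 0.05). The allowance is 5/60 = 8.3%, and it also covers departures from ideal conditions. The rates below are therefore assumptions.

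**3. Patients without a level**

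Of 120 randomised, uncovered withdrawals of 2%, 5%, 10% or 15% leave 2.4, 6, 12 or 18 patients unclassified. For the effect of omitting them, assume level shares of 18/12/10/35/25% and no treatment effect. Omission at random gives an odds ratio of 1.00. Omission only from levels 2 to 4 gives 1.01 (10% versus 5%) and 1.03 (15% versus 5%).

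**4. Deaths placed in levels 4 and 5**

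Assumed true shares for levels 1 to 5 in both arms are 18/12/10/30/30%, so 30% are dead by Day 90. A fraction e is lost before Day 28 and a fraction l of those remaining is lost afterwards, independently of true level. Lost patients are split equally between levels 4 and 5.

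Hidden deaths per 60 = 60 × [0.30e + 0.12(1 − e)l]

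- e = l = 5%: 60 × (0.0150 + 0.0057) = 1.2
- e = l = 10%: 60 × (0.0300 + 0.0108) = 2.4
- e = l = 15%: 60 × (0.0450 + 0.0153) = 3.6

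These compare with 60 × 0.30 = 18 true deaths per arm. The observed shares become 17.1/10.8/9.5/31.3/31.3% at 5%+5%, 16.2/9.7/9.0/32.5/32.5% at 10%+10%, and 15.3/8.7/8.5/33.8/33.8% at 15%+15%.

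A proportional-odds fit to these shares gives the odds ratio for a better level in the arm with more loss:

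| Loss, arm 1 versus arm 2 | Base case | Late-loss rate applied to all of level 2 | Level 3 patients kept in level 3 |
|---|---|---|---|
| 5%+5% versus 5%+5% | 1.00 | 1.00 | 1.00 |
| 5%+5% versus 10%+10% | 1.08 | 1.09 | 1.07 |
| 5%+5% versus 15%+15% | 1.17 | 1.18 | 1.15 |

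Loss after Day 28 alone gives 1.02 (5% versus 10%) and 1.04 (5% versus 15%).

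**5. Against sampling error**

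With 60 per arm, SE(log OR) ≈ √[12 / (120 × (1 − Σp³))]. With Σp³ = 0.0626 this is √0.1067 = 0.33. Since ln 1.17 = 0.16, the largest base-case shift is about half a standard error.

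**The case against.** Much can be said for the plan. Protocol 7.5 intends mortality to be assessed to Day 90, protocol 8.1 asks early discontinuers to attend Day 90, and both flow charts carry a mortality row to that visit, so unknown vital status may be rare. Sending patients lost within 28 days to level 4 or 5 is a stated protocol choice with a reason, and the SAP follows it. The larger odds ratios need total loss of about 30% in one arm and a threefold imbalance. The SAP lists the variable as exploratory, although protocol 12.8.3 calls it secondary, and SAP 6.14 treats secondary and supportive results as descriptive.

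A reader might also infer more than the text supports:

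- *All consent withdrawals are left without a level.* They are not. One with a recorded death, a safety or efficacy reason, a Day 28 MELD, or arguably an early termination MELD after the Day 21 visit is still classified.
- *Patients stopping study drug under protocol 7.5.2 are a second unclassified group.* They remain in follow-up and are expected to have a Day 28 MELD.
- *The SAP excludes patients, declares unknown status to be alive, or abandons the FAS.* It says none of these. Omission and survivor scoring at Day 90 follow from silence and from level definitions that need a death; 6.13.7 simply names no analysis set. A programmer might also read loss to follow-up to include consent withdrawal.

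These points limit the size and reach of the problem. They do not remove it. Planned mortality follow-up reduces unknown status but does not say how to score it. The MAR argument concerns a missing MELD, not a missing death. The route to level 4 or 5 for patients lost before Day 28 is explicit.

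**Conclusion.** The point holds in limited form. The allocation rule does not cover every patient it promises to classify, and following it as written makes a death level unreachable for anyone lost before Day 28 without a recorded death. A patient last known alive before Day 90 counts as a survivor here and as censored in SAP 6.13.1.

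The bias is modest and needs unequal loss. The figures rest on assumed level shares, loss independent of true level, and no treatment effect. They do not support a claim of serious distortion, and the patients left without a level add little in the scenarios tried. The primary endpoint is unaffected. The change is still worth making before unblinding, because the variable is meant to count deaths and the present text leaves the dataset open to more than one construction.

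**What to change.** (a) Replace the sentence on loss to follow-up in SAP 6.13.7 with: *Any FAS patient not in levels 1-3 who has no Day 28 MELD, whatever the reason, is allocated by imputation.* State that the analysis is on the FAS.

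(b) Where vital status at Day 90 stays unknown after the follow-up already planned in protocol 7.5, multiply impute the ordinal level with levels 1 and 2 possible, for example from treatment, baseline MELD and last observed MELD. Level 1 should be possible only if the patient was last known alive before Day 28. The MELD model in 6.11.1 cannot do this, so the imputation model must be named. At the least, add a sensitivity analysis that scores these patients as deaths.

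(c) Tabulate by arm the patients handled under (a) and (b), and record the departure from protocol 12.8.3 in SAP 6.25.

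Cost: SAP wording, a little programming, and a few more imputed values in one secondary or exploratory analysis. No new data collection is needed.
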